To assess the safety and tolerability, adverse events by grade will be summarized. The occurrence of Grade 3+ adverse events according to CTCAE will be summarized as well. Adverse events will initially be reviewed regardless of attribution, but also according to whether adverse events are possibly, probably, or definitely related to treatment. Complete response (CR) at Day 28 among all patients treated and among all patients treated at BETD will be estimated. The proportion of CR with a 95% CI will be reported, assuming a binomial distribution. The overall response rate (ORR) will include CR and partial response (PR), while mixed response (MR) and no response (NR) will be classified as no response. The ORR will be similarly analyzed as CR. To determine 6-month non-relapse mortality (NRM), the event will be death due to reasons other than disease and the time will be measured from the date of starting PLX51107 to date of death with the competing risk as death due to disease (relapse). The cumulative incidence curve accounting for competing risks will be generated to estimate the cumulative incidence of NRM rate at 6 months. The comparison in NRM between patient subgroups may be explored graphically.

Study endpoints

The primary endpoints include:

- To determine the biologically effective and tolerable dose (BETD)
- Safety endpoints (adverse events)
- PK analysis

The secondary endpoints include:

- Preliminary efficacy (CR at Day 28) among all patients treated and among all patients treated at BETD
- Overall response rate (ORR at Day 28) among all patients treated and among all patients treated at BETD
- NRM at 6 months

GVHD Response Definitions

Acute GVHD response will be in comparison to the acute GVHD staging upon Screening. The Mount Sinai Acute GVHD International Consortium (MAGIC) criteria¹⁴ will be used to assess staging and grading. Response will be defined as below (as previously used in BMT-CTN 1802 clinical trial: https://web.emmes.com/study/bmt2/protocol/1802_protocol/1802_protocol.html)

Complete Response (CR) is defined as complete resolution of all signs and symptoms of acute GVHD equivalent to staging 0 in all organs.

Partial Response (PR) is defined as improvement in one or more organs involved at diagnosis/screening and without progression or new acute GVHD symptoms in any organ.

Mixed Response (MR) is defined as improvement in one or more organs involved at diagnosis/screening but with progression or new symptoms in any organ.

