No Response (NR) is defined as no improvement and/or progression of acute GVHD symptoms in any organ.

Number of Subjects

The minimum number of patients accrued to the Phase 1 portion is 6 patients (3 patients with ≥ 2 DLTs at Dose Levels 1 and 0) with maximum of 18 patients (6 patients each at Dose Levels 1-3).

Duration

We anticipate a screen failure rate of approximately 40% and enrolling a maximum 18 patients. The expected time to screen 45 patients at our center would span approximately 2 years. Patients will require at least 6 months of follow-up (6 months after initiation of study drug or 30 days after discontinuation of study drug). Total duration of this trial is expected to take approximately 2.5 years.

Study Calendar

	Cycle 1				Cycle 2				†Cycle 3+	SAE/DLT	*6-mo F/U	EOT	
	Screening	Day 1	Day 8	Day 15	Day 22 ±3	Day 1	Day 8 ±3	Day 15 ±3	Day 22 ±3	Day 1 ±3	±3 days	±7 days	±7 days
Informed Consent/Eligibility Review	X												
Concomitant Medication Review	X		X	X	X	X	X	X	X	X	X	X	X
Physical Exam with Vital Signs	X		X	X	X	X	X	X	X	X	X	X	X
ECOG Performance Status	X		X	X	X	X	X	X	X	X	X	X	X
PLX51107		Daily											
Adverse Event Evaluations		X	X	X	X	X	X	X	X	X	X	X	X
Complete Blood Count (CBC)	X		X	X	X	X	X	X	X	X	X	X	X
Comprehensive Metabolic Panel (CMP)	X		X	X	X	X	X	X	X	X	X	X	X
PT/aPTT/INR	X		X	X	X	X	X	X	X	X	X	X	X
Serum Pregnancy Test	X												
GVHD Staging	X		X	X	X	X	X	X	X	X	X	X	X
Relapse, Survival			X	X	X	X	X	X	X	X	X	X	X
Peripheral Blood for PK		X	X	X									
Peripheral Blood for PD		X	X								X		
†Peripheral Blood for MAP		X	X	X	X	X							
Peripheral Blood for Immune Reconstitution		X	X	X	X	X				X	X	X	X

†Applies to C3D1, C4D1, C5D1, and C6D1

*6 month follow-up may overlap with EOT. In this case, these will be deemed EOT days.

‡MAP refers to MAGIC Algorithm Probability

Please note: $C_n D_{28} = C(n+1)D_1$

Dose limiting toxicity (DLT)

DLTs are defined as AEs or laboratory abnormalities occurring during the first cycle (28 days) of study drug administration that are at least possibly related to PLX51107, deemed to be clearly unrelated to disease progression, concurrent illness or concomitant medication and that meet one of the following NCI CTCAE v5.0 criteria below.

- **Hematological toxicities**
 - Grade >3 neutropenia lasting >7 days
 - Grade ≥ 3 febrile neutropenia
 - Grade 4 thrombocytopenia lasting >14 days despite study drug discontinuation
- **Non-hematological toxicities**

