Doses delayed by more than 2 hours should be skipped. Doses obscured by vomiting should not be re-administered. If more than 7 doses of the first 28 are missed due to noncompliance, the patient will be considered invaluable and study subject replaced. Patients with missed doses removed from evaluation will continue to be monitored for safety.

Duration of Therapy

Dosing is continued until

- 6 months from initiation of study drug. If dose is greater than 20 mg at 6 months, drug should be tapered over maximum one additional month for a maximum of 7 months.
- CR is reached with daily prednisone equivalent \leq 10mg/day. If CR is reached within <6 months, study drug is then tapered by 20 mg over one month.
- toxicity
- relapse of underlying malignancy
- progression of GVHD
- lack of response as defined by No Response in any organ system by Study Day 28
- voluntary withdrawal from study

Duration of Follow-Up

All patients will be followed for up to 6 months from initiation of study drug or 30 days from drug discontinuation (end of treatment, aka EOT) whichever is longer except in the cases of voluntary withdrawal from study or death.

For subjects who withdraw consent, there must be clear documentation of whether the subject withdraws consents to treatment only (i.e. agrees to follow-up) or withdraws consent to treatment and follow-up.

Follow-up

Follow-up appointments will entail review of concomitant medications, physical exam with vital signs, assessment of ECOG performance status, adverse event evaluation, GVHD staging, and assessment for relapse/survival. Labs will also be collected for complete blood count (CBC), comprehensive metabolic panel (CMP), coagulation labs (PT, aPTT, INR). Peripheral blood for PK, PD, ELISA, and immune reconstitution will be collected as above in the Study Calendar and in the Correlative Studies section (below). Patients will be followed weekly for the first two cycles of study drug and monthly thereafter until study drug discontinuation. Additional evaluations will occur at time of SAE or DLT, scheduled 6-month follow-up from initiation of study drug, and end of treatment (30 days from drug discontinuation). All follow-up will be done in-person with the exception of Cycle 2 Days 8, 15, and 22, which may optionally be done via secure video, per the physician's discretion.

Concomitant medications

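### Day 28 response is scored on organ stage alone, so a patient at stage 0 after added GVHD therapy or steroid re-escalation counts as a complete responder

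*Combined protocol and SAP*

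**What the plan says.** Under GVHD Response Definitions the reference point is fixed: "Acute GVHD response will be in comparison to the acute GVHD staging upon Screening". CR is then "Complete Response (CR) is defined as complete resolution of all signs and symptoms of acute GVHD equivalent to staging 0 in all organs". The PR text, cut one word before its end, is "Partial Response (PR) is defined as improvement in one or more organs involved at diagnosis/screening and without progression or new acute GVHD symptoms in any". A mixed response pairs improvement with progression or new symptoms, and no response covers absence of improvement and/or progression. None of the four categories mentions added GVHD treatment or steroid dose.

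The Statistical analysis plan sets the denominator: "Complete response (CR) at Day 28 among all patients treated and among all patients treated at BETD will be estimated". It adds: "The proportion of CR with a 95% CI will be reported, assuming a binomial distribution". On the overall rate, with the last word of the sentence left off: "The overall response rate (ORR) will include CR and partial response (PR), while mixed response (MR) and no response (NR) will be classified as no".

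Other sections bear on who reaches Day 28 and on what treatment:

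- **Duration of Therapy** stops PLX51107 for GVHD progression or toxicity, among other reasons. It does not link that stop to the Day 28 score.
- **Duration of Follow-Up** says "All patients will be followed for up to 6 months from initiation of study drug or 30 days from drug discontinuation"; the longer of the two applies. The Follow-up text just after it ties the weekly and monthly visits to time on study drug.
- **Study Calendar** places GVHD staging and concomitant medication review at Cycle 2 Day 1, which it equates with Day 28.
- **Study Design** gives prednisone 1 mg/kg; **Treatment Plan** (Investigational product) gives 1-2 mg/kg. Both limit how early and how far steroids may be lowered before Day 28. Neither says how an increase is scored.

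**The concern.** The secondary objective is the preliminary efficacy of PLX51107 plus corticosteroids. A Day 28 stage reached after another systemic agent was added, or after steroids were raised following a flare on taper, reflects that extra treatment at least in part. The stated rule credits it to the study regimen.

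There is no control arm in which rescue would act equally, so the reported rate carries the whole effect. Study Design also says clinical responses will be reviewed when the RP2D is justified. In an open-label trial of this size, leaving the scoring of rescued patients until after the data are seen allows a handful of individual decisions to set the result.

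**Working it through.** **1. Denominators.** Number of Subjects gives a design "with maximum of 18 patients (6 patients each at Dose Levels 1-3"). Check: 3 levels × 6 = 18, which reproduces the plan's figure. The BETD rule is stated for 6 patients at a level, so n = 6 there. The plan states no target rate, test or power for CR or ORR, so there is no power figure to reproduce.

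**2. Effect of one patient.** Moving one patient from responder to non-responder changes the rate by 1/n:

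- n = 18: 1/18 = 5.6 percentage points
- n = 6: 1/6 = 16.7 percentage points

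**3. Illustration.** The responder counts and the number rescued, k, are assumptions. Rate = (responders − k)/n, with exact (Clopper-Pearson) 95% intervals.

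| n | Responders by staging alone | k rescued among them | Rate if rescue is failure | 95% CI |
|---|---|---|---|---|
| 18 | 6 | 0 | 6/18 = 33.3% | 13.3-59.0% |
| 18 | 6 | 1 | 5/18 = 27.8% | 9.7-53.5% |
| 18 | 6 | 2 | 4/18 = 22.2% | 6.4-47.6% |
| 18 | 6 | 3 | 3/18 = 16.7% | 3.6-41.4% |
| 6 | 3 | 0 | 3/6 = 50.0% | 11.8-88.2% |
| 6 | 3 | 1 | 2/6 = 33.3% | 4.3-77.7% |
| 6 | 3 | 2 | 1/6 = 16.7% | 0.4-64.1% |

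The k = 0 rows are also what staging-only scoring reports whatever k is. The direction is fixed because k cannot be negative. The intervals overlap heavily, so the issue is a systematic shift in a small, imprecise estimate.

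**4. Who can be rescued and still be staged at Day 28?**

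- A patient still on PLX51107 at Day 28 has a scheduled staging. If steroids were raised again after a taper, or another agent was added, the response text is silent.
- For a patient who stopped PLX51107 on Day s, the end-of-treatment visit falls at s + 30, ±7 days. Stopping on Days 8-14 puts it nominally at Days 38-44, or Days 31-51 with the window. That window runs from s + 23 to s + 37 and includes Day 28 only if s ≤ 28 − 23 = 5. Later stoppers have no scheduled Day 28 staging unless an SAE or DLT visit, or a routine inpatient assessment, happens to fall then.

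The definition therefore has two gaps: rescued patients who are assessed at Day 28, and patients with no Day 28 assessment.

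**The case against.** Several points on the other side are sound and limit the claim.

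- **Early stoppers.** A reader might infer that a patient who progresses in week 2, stops drug and is rescued will be staged 0 at Day 28 and counted as a CR. The visit schedule does not support that as the expected course, as the window arithmetic shows. For such patients the open question is how a missing assessment is scored.
- **Death and relapse.** A reader might infer that these also inflate response. A patient who has died cannot be at stage 0 or show improvement, and stays in the all-treated denominator. On relapse, the Differentiation Syndrome section stops drug and withdraws the patient.
- **PR.** The requirement of no progression could mean at any time, which would make many rescued progressors mixed or non-responders. It could equally mean Day 28 against Screening, the stated comparison. The gap is therefore less clear for PR. CR carries no such condition.
- **Silence.** No text says outright that rescued patients count. The text under Withdrawal is not in the copy reviewed and may hold a related rule, and the definitions cite another trial's protocol that cannot be checked here. Still, the plan writes its definitions out in full and points to no rescue rule.
- **Steroids are part of the regimen.** Steroid use within the planned dose is not rescue. The point concerns increases for GVHD, and these cannot be defined until the 1 mg/kg and 1-2 mg/kg statements agree.
- **Secondary and descriptive.** There is no test or threshold on CR or ORR, and the BETD rests on DLTs and PK exposure.

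After all this, a patient assessed at stage 0 on Day 28 after added systemic therapy or steroid re-escalation still meets the CR definition as written.

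**Conclusion.** The point holds for patients who are assessed at Day 28: clearly for CR, less clearly for PR. The size is 5.6 points per such patient among 18 and 16.7 points among 6, always upward relative to counting rescue as failure. The total shift depends on how many patients are rescued before Day 28, for which the documents give no figure; the tabulated counts are illustrations only.

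What is affected is the interpretation of the secondary efficacy estimates and the clinical-response part of the RP2D review. A reader might infer that the BETD itself is biased; it is not, because it does not use clinical response. A staging-only rate is a legitimate quantity, but it describes outcome under whatever treatment followed. It does not isolate response to PLX51107 plus corticosteroids, which is the stated objective.

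**What to change.** Add to GVHD Response Definitions, and refer to it in the Statistical analysis plan:

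> For CR and ORR at Day 28, a patient is counted as a non-responder, and remains in the all-treated denominator, if before the Day 28 assessment the patient starts new systemic treatment for acute GVHD, has corticosteroids increased for GVHD from the dose then being taken (including re-escalation after a taper), or if there is no Day 28 assessment. The rate based on staging alone will be reported as a sensitivity analysis.

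Three details go with it:

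- Measure an increase from the dose then being taken. A comparison with the Day 1 dose would miss a patient who flares on taper and returns to that dose.
- Reconcile the steroid dose statements in Study Design and Treatment Plan so that an increase is defined for scoring. This is a scoring rule only and takes no position on which dose is right.
- State which visit window counts as the Day 28 assessment, and that level-guided adjustment of ongoing GVHD prophylaxis is not new treatment.

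Cost: a short text change, with no effect on treatment or sample size. Concomitant medication is already reviewed at scheduled visits from Day 8 for patients on drug. For a patient off drug who is nevertheless staged at Day 28, it should be recorded at that assessment. The downside is a possibly slightly lower reported rate, including some patients who count as failures only because they were not assessed. Tabulating non-responders by reason would make that visible.

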 - New onset non-hematological clinical and laboratory toxicity grade ≥ 3 lasting >72 hours with the exception of the following events:
 - Grade ≥ 3 nausea, vomiting or diarrhea that resolves to grade ≤ 2 within 72 hours, with maximal medical intervention
 - Grade 3 fatigue, asthenia, anorexia, fever or constipation that resolves to grade ≤ 2 within 14 days
 - Grade ≥ 3 asymptomatic changes in alkaline phosphatase, hypomagnesemia, hyperglycemia or hypophosphatemia
 - Grade 3 increases in transaminases confirmed upon repeat testing lasting ≤ 5 days
 - Any Grade ≥ 3 electrolyte abnormality that is corrected to Grade ≤ 2 within 24 hours
 - Non-hematologic laboratory Grade 3 AE that is asymptomatic and/or rapidly reversible (returned to baseline or to Grade ≤ 1 within 7 days) unless identified as clinically relevant by the Investigator; and (in non-diabetic patients) singular or non-fasting elevations in blood glucose
 - Any case of Hy's law defined as AST or ALT $>3 \times$ ULN with concurrent total bilirubin $>2 \times$ ULN, absence of cholestasis (elevated ALP $>2 \times$ ULN), and no alternative etiology, which can explain the combination of increased AST or ALT and total bilirubin, such as viral hepatitis A through E, other preexisting or acute liver disease, liver acute GVHD, or another drug capable of causing the observed injury
 - Any dose reduction required during Cycle 1 due to grade ≥ 3 adverse events
 - Any treatment delay of >7 consecutive days during Cycle 1 due to study drug-related Grade ≥ 3 adverse events that fails to resolve to baseline or grade ≤ 1
 - Any Grade ≥ 3 gastrointestinal, genitourinary or central nervous system hemorrhage
 - Any grade 4 or 5 nonhematological adverse reaction
 - Any death unless unequivocally due to underlying disease (or extraneous cause)

Any adverse reaction unrelated to active GVHD that leads to the study drug PLX51107 dose reduction or withdrawal should be considered a DLT.

Grade 3 or higher adverse events occurring past 28-days must be recorded and reviewed for final analysis and for Phase 2 dose evaluation.

Hold Parameters

		Occurrence	Resume	Dose
Neutropenia	Grade 4 (ANC <500/mm3)	1st	Upon improvement to Grade ≤2 (ANC >1000/mm3). GCSF support may be used.	If improved within 7 days, continue same dose. If no improvement within 7 days, permanently discontinue drug.

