		2nd	Upon improvement to Grade ≤2. GCSF support may be used.	If improved within 7 days, dose reduce by one level. If no improvement within 7 days, permanently discontinue drug.
		3rd	Permanently discontinue study drug.	
Thrombocytopenia	Grade 4 (platelet count <25,000/mm3)	1st	Upon improvement to Grade ≤2 (platelet count >50,000/mm3) within 14 days	If improved within 14 days, continue same dose. If no improvement within 7 days, permanently discontinue drug.
		2nd	Upon improvement to Grade ≤2 (platelet count >50,000/mm3) within 14 days	If improved within 14 days, dose reduce by one level. If no improvement within 7 days, permanently discontinue drug.
		3rd	Permanently discontinue study drug.	
Other non-hematologic	Grade 3 adverse events	1st	Hold until improved to Grade ≤1	If improved within 5 days, continue same dose. If >5 days, dose reduce by one level.
		2nd	Hold until improved to Grade ≤1.	If improved within 5 days, dose reduce by one

				level. If >5 days, permanently discontinue.
Other non-hematologic	Grade 4 adverse events	1st	Permanently discontinue study drug	

Treatment Plan

Investigational product

PLX51107 will be supplied by Plexxikon in 20 mg tablet formulations. Each participating site must have sufficient supply for one cycle (28 days) available prior to enrollment of each patient. Additional months' supplies will be ordered by the site accordingly.

All patients will receive prednisone 1-2 mg/kg orally daily (may be divided into 2 doses) or MP IV equivalent. Corticosteroids may be tapered per institutional guidelines but initiated no sooner than 7 days after Study Day 1 and to no less than prednisone 0.25mg/kg daily before Study Day 28. The minimum dose of prednisone at Study Day 1 is 1mg/kg (or MP IV equivalent).

Treatment Dosage and Administration

The first day of administration is deemed Study Day 1. The dosage administered is determined by dose level in Table 1 and in observance of DLT or SAE considerations.

Treatment will be administered orally daily. The first day of administration is Study Day 1. PLX51107 should be taken at approximately the same time of day. On Study Days 1, 8, and 15 when PK/PD sample collections are drawn, patients should fast 8 hours prior and 1 hour after daily dose administration. On other days when, there are no scheduled PK/PD sample collections, patients should fast 2 hours prior and 1 hour after daily dose administration.

Dosing Delays or Missed Doses

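### Several DLT exemptions are partly overridden by other DLT lines read with the hold table, and the plan does not say which governs

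*Combined protocol and SAP*

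**What the plan says.** The section Dose limiting toxicity (DLT), repeated in the Synopsis, counts first-cycle events that satisfy its relatedness conditions and "that meet one of the following NCI CTCAE v5.0 criteria below". The first non-hematological criterion is "New onset non-hematological clinical and laboratory toxicity grade ≥ 3 lasting >72 hours with the exception of the following events", followed by six exceptions. One is "Grade 3 fatigue, asthenia, anorexia, fever or constipation that resolves to grade ≤ 2 within 14 days". Three are worded to include Grade 4: "Grade ≥ 3 nausea, vomiting or diarrhea that resolves to grade ≤ 2 within 72 hours, with maximal medical intervention"; asymptomatic changes in alkaline phosphatase, magnesium, glucose or phosphate; and "Any Grade ≥ 3 electrolyte abnormality that is corrected to Grade ≤ 2 within 24 hours".

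Further DLT criteria follow, none of which sets exempt events aside: "Any dose reduction required during Cycle 1 due to grade ≥ 3 adverse events"; a Cycle 1 treatment delay beyond 7 days for a drug-related Grade 3 or higher event that does not recover; and "Any grade 4 or 5 nonhematological adverse reaction". A closing sentence also makes a DLT of any reaction not related to active GVHD that causes dose reduction or withdrawal.

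The Hold Parameters table holds drug for a Grade 3 non-hematologic adverse event until Grade 1 or lower. At the first occurrence the instruction is "If improved within 5 days, continue same dose. If >5 days, dose reduce by one level". At the second, the dose is reduced even with improvement inside 5 days, and drug is stopped otherwise. A Grade 4 non-hematologic adverse event means permanent discontinuation.

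Under Study Design, a level can be the BETD only with at most one DLT in six patients; two DLTs stop the level and lead to de-escalation.

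**The concern.** The exemption list and the hold table use different recovery grades and different clocks, and the consequence of the hold table feeds back into the DLT list. One clinical course can therefore be excepted by one line and counted by another. DLT status is half of the BETD rule, and the BETD is the first primary endpoint listed, so unclear status carries straight into the dose decision. With six patients and a limit of one DLT, a single disputed patient can decide it.

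**Working it through.** **Plan's own figures.** The only design numbers tied to the DLT rule are minimum and maximum accrual: 3 + 3 = 6 (two levels of three) and 3 × 6 = 18 (three levels of six). Both reproduce. No target DLT rate or operating characteristic is given, so there is no stated probability to check.

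**Lines side by side** (Cycle 1, relatedness conditions met):

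| Course | Exemption list | Hold table | Other DLT lines |
|---|---|---|---|
| First Grade 3 fatigue, Grade 2 on day 4, Grade 1 on day 8 | Exempt (14-day line) | Over 5 days to Grade 1: reduce | DLT by reduction |
| First Grade 3 fatigue, Grade 1 on day 5 | Exempt | Same dose | None: stays exempt |
| Second Grade 3 fatigue, Grade 1 on day 4 | Exempt | Reduce | DLT by reduction |
| Grade 4 electrolyte adverse event, Grade 2 or lower within 24 h | Exempt | Discontinue | DLT by the Grade 4 line and the withdrawal sentence |
| Grade 4 thrombocytopenia, no improvement by day 7, resolved by day 14 | Below the DLT threshold (more than 14 days) | Discontinue at 7 days | Can be a DLT by the withdrawal sentence |

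The table takes improvement in the hold rules to mean the resume grade, Grade 1 or lower. In the thrombocytopenia row, the hold table also speaks of continuing if improved within 14 days.

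**Day count for the fatigue-type exemption, first occurrence.** Let t be the day Grade 1 or lower is reached, and assume the event passes Grade 2 the same day. Beyond 72 hours and within the allowance, t = 4, …, 14, which is 11 durations.
- t = 4–5: 2 of 11 keep the same dose and stay exempt.
- t = 6–14: 9 of 11 require a reduction and so meet a DLT line.
- t = 8–14: 7 of these 9 may also meet the treatment-delay line.

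These are counts of possible durations, not probabilities. The general Grade 3 laboratory exemption (recovery within 7 days) behaves alike where the value is an adverse event: days 4–5 are clear, days 6–7 conflict.

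**What the short exemptions do.** The parent criterion needs Grade 3 or higher for more than 72 hours. An event at Grade 2 or lower within 72 h (nausea, vomiting, diarrhea) or 24 h (electrolytes) never meets it, so these two exceptions do no work against the only criterion they are attached to.

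**Effect on the tolerability half of the BETD rule.** For six independent patients with per-patient DLT rate p, P(at least 2 of 6) = 1 − (1−p)^6 − 6p(1−p)^5. The rates are assumptions.
- p = 0.10: 1 − 0.531441 − 0.354294 = 0.114
- p = 0.20: 1 − 0.262144 − 0.393216 = 0.345
- p = 0.30: 1 − 0.117649 − 0.302526 = 0.580

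If 10% of patients had an undisputed DLT and a further 10% or 20% had only a disputed event, the chance that a level fails would be 0.114 with the disputed events exempt, and 0.345 or 0.580 with them counted.

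**The case against.** The strongest reply is that the text already has a literal answer. Meeting any one criterion is enough, and the exceptions belong only to the 72-hour criterion; in the Synopsis they are sub-bullets, while dose reduction, delay and Grade 4–5 reactions are separate bullets. An event excepted from one criterion may still meet another without formal contradiction, and the disputed events are then DLTs. That reading is available. However, it leaves the 14-day allowance largely without effect after day 5 and the Grade 4 part of three exemptions void, and two exemptions are redundant against their own parent criterion. It is hard to take that as the intent, and no sentence says so.

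Other parts of the reply stand and limit the point. A reader might infer that the exemptions are cancelled altogether. They are not: a first Grade 3 event back to Grade 1 or lower within 5 days remains exempt. Under Adverse Events and Adverse Event Management, a laboratory value that causes no symptoms, is not judged clinically significant and needs no therapy is not an adverse event, so it triggers no hold. A DLT must also be clearly unrelated to disease progression, concurrent illness or concomitant medication, which narrows the disputed pool. The Cycle 1 reduction line applies only if the reduction falls in Cycle 1.

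A reader might also infer that two sites could reach opposite dose decisions. The documents do not describe that: slots and registration are central, the principal investigator reviews toxicities, and all-site calls are at least monthly. Inconsistent scoring of similar courses is possible; separate dose decisions by site are not part of the design.

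Finally, rules for holding drug and rules for defining a DLT may legitimately differ. The fault is the missing statement of how they interact, not the difference itself.

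**Conclusion.** Wrong as written: an internal inconsistency in the DLT rule behind a primary endpoint. The exemptions are partly overridden, chiefly for fatigue-type Grade 3 events that take 6 or more days to reach Grade 1, repeat Grade 3 events, and Grade 4 events under the three broader exemptions. Grade 4 thrombocytopenia has a parallel problem.

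The direction is certain, since counting disputed events can only raise the DLT count. The size is not known: it depends on how often disputed events occur, for which the documents give no rate. The probabilities above also assume independence and six patients at the level, whereas a level starts with three. What needs no assumption is that one reclassified patient can move a level from one DLT to two.

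**What to change.** Reconcile the exemption list, the dose-reduction line, the Grade 4–5 line, the reduction-or-withdrawal sentence and the Hold Parameters table, in both the Synopsis and the DLT section. In the DLT section, state one order of precedence that settles the status of an exempt event, or one below a DLT duration threshold, when it triggers a protocol-mandated reduction or discontinuation or reaches Grade 4. Do this before further DLTs are adjudicated.

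In the BETD report, give the number of DLTs per level under that rule and list each event whose status turned on it.

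Which reading governs, and whether any recovery grade or day limit changes, is for the sponsor and investigators. The cost is a wording amendment, with no added patients or procedures; the DLT count at a level may change.
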